4.2 Scientific Rationale for Study Design

Screening Cycle: Visit 2 to Visit 3

Participants will be dispensed an eDiary and rescue medication at Visit 2 and instructed on their use. The information collected during the SC will allow the investigator to ascertain and verify that the participant meets requirements for study entry (ie, length of menstrual

cycle, average pelvic pain score, compliance with eDiary entries, and compliance with rescue and other pain relief medications) as noted in the Inclusion Criteria (Section 5.1).

Baseline Cycle: Visit 3 to Visit 4/Day 1

At Visit 3, single-blind placebo run-in medication will be dispensed. Thus, in addition to continued monitoring to ensure the participant meets inclusion criteria as noted above, this baseline menstrual cycle has the purpose of familiarizing the participants with the study treatment regimen and excluding participants with a placebo response (ie, participants who have an average pain score during the SC of ≥ 5 , and average pain score during the BC of < 5 , as measured by the NRS in the Daily eDiary). In addition, participants who are not compliant with the blinded placebo before randomization will be excluded. Baseline measurements for change from baseline analyses will be obtained during this cycle.

Treatment Cycle 1 and 2: Visit 4/Day 1 to Visit 6

TRC1 and TRC2 provide 2 complete menstrual cycles to evaluate the safety and efficacy of MK-7264. Two cycles have been proposed as an adequate timeframe for the efficacy of the medication to be observed. The primary efficacy will be assessed by the change from baseline in average daily pelvic pain score (cyclic and non-cyclic) during TRC2. Efficacy will also be assessed at TRC1 via an exploratory objective.

Post-treatment Cycle: Visit 6 to Visit 7

The purpose of the PTC is to assess the pain scores after participants have stopped double-blind study intervention. Pain scores from the PTC will be compared to pain scores from the SC, as the participants will be under the same clinical circumstances (ie, only rescue medication being used as needed) during both cycles.

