The first exploratory endpoint is the average daily use of naproxen sodium rescue medication by number of tablets taken for daily pelvic pain (cyclic and non-cyclic, combined and separately) during TRC2, as compared to the BC. Rescue medication use and the difference in usage between the MK-7264 and placebo treatment groups will be indicators of treatment efficacy in pain control.

The proportion of participants with at least 1-point reduction in average daily pelvic pain score (cyclic and non-cyclic, combined and separately) as compared to baseline during TRC2 is another exploratory endpoint. This endpoint is to evaluate the proportions of participants who have had pain reduction from the study intervention irrespective of analgesic use. However, to further evaluate that pain reduction is not due to use of analgesics, composite endpoints with reduction in pelvic pain and no increased use of rescue medication or other analgesic use will be evaluated. Therefore, the following exploratory endpoints will also be evaluated for this purpose:

- The proportion of participants with at least 1-point reduction in average daily pelvic pain score (cyclic and non-cyclic, combined and separately) as compared to baseline during TRC2, and no increase in average daily use of rescue medication by number of tablets;
- The proportion of participants with at least 1-point reduction in average daily pelvic pain score (cyclic and non-cyclic, combined and separately) as compared to baseline during TRC2, and no increase in average daily use of rescue medication, and no use of concomitant pain medication;
- The proportion of participants with at least 1-point reduction in average daily pelvic pain score (cyclic and non-cyclic, combined and separately) as compared to baseline during TRC2, and no increase in average daily use of rescue medication, and no use of concomitant pain medication for ERP.

While this study is designed to further explore the clinical importance of changes in pelvic pain score, for this PoC study, a 1-point reduction in average daily pelvic pain is the

minimum that will be considered clinically meaningful. Reductions greater than 1-point (ie, 2-point and 3-point reductions) will also be analyzed as part of this objective.

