11. Participant has an estimated glomerular filtration rate <50 mL/min/1.73 m² (using the Chronic Kidney Disease Epidemiology Collaboration [CKD EPI] formula) at Visit 1.
12. Participant has systolic blood pressure >160 mm Hg or diastolic blood pressure >90 mm Hg at Visit 1.
13. Participant is, at the time of signing informed consent, a user of recreational or illicit drugs or has had a recent history (within the last year) of drug or alcohol abuse or dependence, per the investigator's discretion. Participants are asked to follow the protocol-specified restrictions on alcohol use during the study (Section 5.3.1).
14. Participant has a history of ERP that was non-responsive to treatment with CHCs, GnRH antagonists, GnRH agonists, progestins, or aromatase inhibitors.

Note: Participants who achieved a partial response or were treatment failures due to side effects should not be excluded.

15. Participant has a history of malignancy ≤ 5 years before signing informed consent except for adequately treated basal cell or squamous cell skin cancer or in situ cervical cancer.
16. Participant has donated or lost ≥ 1 unit of blood (approximately 300 mL) within 8 weeks before the first dose of MK-7264.
17. Participant has a positive urine pregnancy test at any time before randomization. If the urine test cannot be confirmed as negative, a serum pregnancy test is required. In such cases, the participant must be excluded from participation if the serum pregnancy result is positive.

Prior/Concomitant Therapy

18. Participant has required more than 2 weeks of continuous use of narcotics for treatment of ERP within 6 months of Visit 1.
19. Participant has received any treatment listed in [Table 1](#) more recently than the "Last Allowable Use" as indicated in the table, or must continue to receive any treatment listed in [Table 1](#) during the study.

Table 1 Prohibited Medications and Other Substances

Prohibited Medications¹: Hormones	Last Allowable Use
GnRH agonists with 1-month duration or GnRH antagonists, aromatase inhibitors, menotropins and human chorionic gonadotropin (hCG)	3 months before Visit 1
Injectable GnRH agonist with 3-month duration (eg, leuprolide)	10 months before Visit 1
Oral, patch, and implanted contraceptives; vaginal ring, and medicated intrauterine device (IUD); oral progestins (eg, norethindrone acetate and dienogest)	2 months before Visit 1 ²
Injectable hormonal contraception with 1-month duration	3 months before Visit 1

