Injectable hormonal contraception with 2-month duration	6 months before Visit 1
Injectable hormonal contraception with 3-month duration; injectable medroxyprogesterone acetate; injectable depomedroxyprogesterone acetate	9 months before Visit 1
IUD (non-hormonal)	Before Visit 1 ³
Prohibited Medications¹: Analgesics	Last Allowable Use

 • NSAIDs (eg, aspirin, ketorolac) 
 ○ Protocol-specified naproxen sodium rescue medication is permitted. • COX-2 inhibitors • Other non-specified analgesics (eg, acetaminophen or paracetamol) 	At Visit 2 ⁴

 • Opioid analgesics (eg, tramadol and tapentadol) 	5 days before Visit 2
Prohibited Medications¹: Other	Last Allowable Use

 • Herbal remedies containing Hypericum perforatum (eg, Kava kava and St. John's wort) • Glucocorticoids (oral or intravenous) • Anti-Tumor Necrosis Factor (TNF)/Anti-Nerve Growth Factor (NGF) 	At Visit 1 2 months before Visit 1
¹ Excluded from the time point specified above and throughout the study. ² Not including emergency contraceptive pills. ³ Intrauterine device (non-hormonal) must be removed before the day of screening visit. ⁴ Short term use (ie, ≤3 days) of non-opioid pain medications for acute conditions (other than ERP) is permitted.	

Prior/Concurrent Clinical Study Experience

20. Participant has received MK-7264 in a previous clinical study.
21. Participant is currently participating in or has participated in an interventional clinical study with an investigational compound or device within 30 days of participating in the current study.

Diagnostic Assessments

22. Participant has clinically significantly abnormal laboratory tests at Screening, including:
 - a. Alkaline phosphatase (AP), alanine aminotransferase (ALT, SGPT), aspartate aminotransferase (AST, SGOT) >200% of the upper limit of normal, or total bilirubin >150% of the upper limit of normal.
 - b. Hemoglobin <10 gm/dL, white blood cell count <2500 mm³, neutrophil count <1500 mm³, platelet count <100 × 10³/mm³.

Other Exclusions

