6.5 Concomitant Therapy

Medications specifically prohibited in the exclusion criteria are not allowed from the time specified for each medication in [Table 1](#) (Section 5.2) until early discontinuation or end of the post-treatment period. If there is a clinical indication for any medication or vaccination specifically prohibited, discontinuation from study intervention may be required. The investigator should discuss any questions regarding this with the Sponsor Clinical Director. The final decision on any supportive therapy rests with the investigator and/or the participant's primary physician. However, the decision to continue the participant on study intervention requires the mutual agreement of the investigator, the Sponsor, and the participant.

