8.10.5 Discontinued Participants Continuing to be Monitored in the Study

If a participant is discontinued from the study intervention early, the Discontinuation Visit assessments are to be performed as indicated in the SoA.

It is intended that all randomized participants should be followed through completion of the study, regardless of premature discontinuation of treatment, unless the participant withdraws consent from any study follow-up. Thus, participants who discontinue from study intervention before completion of the study should continue to be monitored after the Discontinuation Visit to obtain relevant information through the end of the study.

After the Discontinuation Visit, a telephone contact will be conducted 14 days following cessation of double-blind study intervention during which all reportable safety events as outlined in Section 8.4, [Table 3](#) will be collected. After the 14 day telephone contact, only drug-related SAEs will be collected; in addition, if the investigator becomes aware of any AEs (serious or non-serious) assessed as related to the rescue medication (naproxen sodium), they must be reported to the Sponsor.

Study site visits (or telephone contacts if scheduling of site visits is not possible) should occur at timepoints that correspond to each remaining study visit on the SoA. Only safety events as specified in the paragraph above and concomitant medication information will be collected at these visits. In addition, participants will be asked to continue to provide daily eDiary entries after discontinuation of study intervention; however, if a participant does not agree to continue using the eDiary, she will still be followed for collection of safety events as specified above and concomitant medication information.

Concomitant therapies specifically prohibited (see [Table 1](#)) while the participant was on study intervention are no longer prohibited after discontinuation of study intervention.

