9.6.1 Statistical Methods for Efficacy Analyses

This section describes the statistical methods that address the primary and secondary objectives. The primary analysis will be based on the FAS population, and supportive analyses will be based on the mFAS, Completer population and PP population.

The primary efficacy endpoint is the average daily pelvic pain score during TRC2. The variable of change from baseline in the average daily pelvic pain score will be used in the analysis of the primary endpoint. The primary analysis approach will be conducted utilizing the longitudinal analysis of covariance (ANCOVA) model. In this model, the response vector consists of the change from baseline in the average daily pelvic pain scores during TRC1 and TRC2. The model will include factors for average pelvic pain scores at baseline cycle, stratum, treatment, cycle, interaction of stratum-by-cycle, and the interaction of treatment-by-cycle as covariates. The model will use all available daily scores for calculating average pain scores during TRC1 and TRC2. The least-squares (LS) mean change from baseline at TRC2 with the associated standard errors (SEs) will be displayed for each treatment group; and the estimated treatment differences (MK-7264 – placebo) along with corresponding 95% CIs will also be presented.

The average daily pelvic pain score during TRC1 will be analyzed from the same model, and the LS mean (SEs, and 95% CIs) will be presented in the same way.

The secondary endpoints will be analyzed in the same way as the primary endpoint.

[Table 4](#) summarizes the key analyses strategies of the primary and secondary efficacy endpoints.

Table 4 Statistical Methods for Efficacy Endpoints

Endpoint/Variable (During TRC2)	Approach	Statistical Method	Analysis Population	Missing Data Approach
Primary				
Average daily pelvic pain scores during TRC2	P	Longitudinal ANCOVA	FAS	Observed data only
	S	Longitudinal ANCOVA	mFAS/Completer Population/PP	Observed data only
	S	Longitudinal ANCOVA	FAS	Jump to reference imputation
Secondary				
Average daily cyclic pelvic pain scores during TRC2	P	Longitudinal ANCOVA	FAS	Observed data only
	S	Longitudinal ANCOVA	mFAS/Completer Population/PP	Observed data only
	S	Longitudinal ANCOVA	FAS	Jump to reference imputation
Average daily non-cyclic pelvic pain scores during TRC2	P	Longitudinal ANCOVA	FAS	Observed data only
	S	Longitudinal ANCOVA	mFAS/Completer Population/PP	Observed data only

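### Hormonal therapy started after study drug is stopped passes the three composite responder definitions, and no stated rule for the FAS, mFAS, per-protocol or jump-to-reference analyses separates the later pain scores

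*Combined protocol and SAP*

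**What the plan says.** **After study drug stops.** Protocol Section 8.10.5 says that concomitant therapies barred by Table 1 "while the participant was on study intervention are no longer prohibited after discontinuation of study intervention". Section 6.5 agrees: the ban runs "until early discontinuation or end of the post-treatment period". Among the hormones in Table 1 (Section 5.2) are "Oral, patch, and implanted contraceptives; vaginal ring, and medicated intrauterine device (IUD); oral progestins (eg, norethindrone acetate and dienogest"; under a separate analgesic heading it lists "Opioid analgesics (eg, tramadol and tapentadol". Section 8.10.5 also says that "participants will be asked to continue to provide daily eDiary entries after discontinuation of study intervention".

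**Which scores are analysed.** Section 9.6.1 states: "The model will use all available daily scores for calculating average pain scores during TRC1 and TRC2". In sSAP 3.6.1, TRC2 is bounded by bleeding days and carries no dosing condition.

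**Responder endpoints** (protocol Section 3, sSAP 3.6.1). Definition 1 is a fall of at least 1 point whatever analgesics are used. Definition 2 adds no increase in rescue tablets. Definition 3 further adds no concomitant pain medication. Definition 4 is like 3 but limits that last condition to pain medication for endometriosis-related pain (ERP). Section 4.2.1.1 gives the reason for definitions 2 to 4: to check that the fall in pain is not caused by analgesics, "composite endpoints with reduction in pelvic pain and no increased use of rescue medication or other analgesic use will be evaluated".

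**Post-treatment Cycle (PTC).** Section 4.2 justifies comparing it with the Screening Cycle (SC) "as the participants will be under the same clinical circumstances (ie, only rescue medication being used as needed) during both cycles".

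**Text pointing the other way.** Table 1 footnote 1 excludes the listed treatments for the whole study. Appendix 5 does not permit hormonal contraception during the study, apart from sporadic emergency use.

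**The concern.** A woman may stop study drug, for example because of taste effects, start a hormonal endometriosis therapy and go on recording pain. Her TRC2 average is then analysed under her randomised arm and may partly reflect the new therapy. The composites exist to rule out one competing explanation for a fall in pain, analgesic use. Hormonal treatment is another, and nothing in the definitions catches it.

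The plan has reason to expect more stopping on active drug. Section 4.3.3 reports that 10% of participants at 50 mg bid in a chronic cough trial discontinued for taste effects, and it names taste disturbance as a possible cause of dropout here. If stopping is unequal, so may be the benefit gained from other therapy.

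**Working it through.** **1. Does any analysis set or method separate these scores?**

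| Analysis | Stated rule | Separates them? |
|---|---|---|
| FAS | one dose, one post-randomisation diary day | no |
| mFAS | one dose, 10 diary days in each treatment cycle | no |
| Per-protocol | names diary compliance under 75% and no TRC2 scores; list is open | not by any stated criterion |
| Completer (also used at the interim) | completed TRC2 | ambiguous |
| Jump-to-reference | imputes when a cycle has no diary entry | no, if the diary is kept |

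The completer entry is ambiguous because protocol Section 4.1 links completing TRC2 with the end of study intervention, while the jump-to-reference formula in sSAP 3.6.1 takes completers to be those with a non-missing response.

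**2. Who can pass the responder definitions?** Each woman is assumed to improve by at least 1 point with no increase in rescue tablets.

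| Therapy started after stopping drug | Def. 1 | Def. 2 | Def. 3 | Def. 4 |
|---|---|---|---|---|
| Hormone | pass | pass | pass | pass |
| Opioid for ERP | pass | pass | fail | fail |
| Opioid for another reason | pass | pass | fail | pass |

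Concomitant pain medication is not defined, but Section 4.2.1.1 speaks of analgesics and Table 1 lists hormones apart from them. Section 6.5.1 provides study naproxen only until early discontinuation, so the rescue condition may be met simply because supply has ended.

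**3. The plan's own figure.** With 70 per arm, SD 2 and a difference of 1 point, SE = 2 × √(2/70) = 0.338. Then 1/0.338 − 1.96 = 1.00, so power is 84%, as stated.

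**4. Shift in the primary difference.** The documents give no switching rate, so every input here is an assumption. Let dA and dP be the shares that stop drug but keep the diary in the active and placebo arms, s the share of these who start such therapy, and h its benefit in points.

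Shift = (dA − dP) × s × h

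- Low: (0.10 − 0.03) × 0.25 × 1 = 0.0175, about 0.02 point.
- High: (0.15 − 0.05) × 0.50 × 2 = 0.10 point.
- Equal stopping (dA = dP): 0.

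With 83 per arm, SE = 2 × √(2/83) = 0.31, so the shift is 0.06 to 0.32 SE. If the drug has no effect, the chance of a significant result in its favour rises from 2.5% to between 2.9% and 5.1%.

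**5. If the drug works.** Suppose its on-treatment effect is D and is lost on stopping.

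Difference = (1 − dA) × D + (dA − dP) × s × h

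With D = 1:
- Low: 0.90 + 0.0175 = 0.92.
- High: 0.85 + 0.10 = 0.95.
- High case, but with every stopper switching (s = 1): 0.85 + 0.20 = 1.05.

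In the first two cases dilution exceeds the gain; in the third it does not.

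**6. Excess responders on drug.** If every starter becomes a responder only because of the therapy, the excess is 0.07 × 0.25 = 1.75 percentage points up to 0.10 × 0.50 = 5 points. That is a ceiling. With SD 2 and mean change 0, the chance of a fall of at least 1 point is 0.31; a benefit of 1 or 2 points raises it to 0.50 or 0.69, a gain of 0.19 or 0.38. The excess is then 0.0175 × 0.19 = 0.3 points up to 0.05 × 0.38 = 1.9 points.

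**7. Would jump-to-reference reveal it?** The sSAP estimate is π × δ, with π the share of the drug arm with a TRC2 response. If 15% have none and δ = 1, it is 0.85. If all who stop keep the diary, π = 1 and it equals the primary estimate.

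**The case against.** Following every randomised woman and analysing what she records is a legitimate treatment-policy choice. This stands, and the primary analysis should not change.

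Several stronger readings are tempting but unsupported:

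- A reader might infer that the composites were meant to exclude every other treatment. Section 4.2.1.1 speaks only of analgesics, and the composites do what it says. The gap is that hormones fall outside that filter.
- A reader might infer that opioid starters slip through in the same way. They fail definition 3, and definition 4 if the opioid is for ERP.
- A reader might infer that every efficacy analysis is affected. The per-protocol list is open and the completer definition is unclear. PGIC and the second EHP-5 are scheduled at Visit 6 or the discontinuation visit, so they are not exposed in the same way.
- A reader might infer that the bias must favour drug. Placebo women in poorly controlled pain may also switch, the placebo stopping rate assumed above has no source in the documents, and dilution works the other way.

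The conflicting text also bears on the premise. Table 1 footnote 1 and Appendix 5 read as continuing bans, and inclusion criterion 7 keeps contraceptive guidance in force for at least 14 days after the last dose in women who discontinue.

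**Conclusion.** The point holds in limited form. As Sections 6.5 and 8.10.5 are written, a woman can start hormonal endometriosis therapy after stopping drug, keep her diary, and count as a responder in all three composites. She also counts under definition 1, which is unfiltered by design. No stated rule for the FAS, mFAS, per-protocol or jump-to-reference analyses separates her scores.

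The size is modest and rests wholly on assumed rates: about 0.02 to 0.10 point on the primary difference if more women stop on drug, none if stopping is equal, and possibly less than the dilution if the drug works. The 2 to 5 percentage-point responder excess is an upper limit. This does not invalidate the primary analysis. It is a definitional gap in exploratory endpoints, and the planned sensitivity analysis would not show it. The PTC rationale likewise fails for any woman who has started such therapy.

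**What to change.** Keep the treatment-policy primary analysis and leave the clinical rules as they are.

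1. In the three composite responder endpoints (sSAP 3.6.1), count a woman who started a Table 1 hormonal or opioid therapy before the end of TRC2 as a non-responder.
2. If a supportive analysis is added, set the whole cycle average to missing for any treatment cycle in which, or before which, such therapy was started, and impute it by the planned jump-to-reference method. Deleting single days would not work. A woman who starts mid-cycle keeps her earlier entries, so nothing would be imputed for the combined score. Because cycles end with menses, the lost days would be mostly menstrual.
3. In the PTC-versus-SC comparison, exclude women who started such therapy before or during the PTC.
4. Reconcile Table 1 footnote 1 and Appendix 5 with Sections 6.5 and 8.10.5 on whether these therapies are allowed after discontinuation.

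Items 1 to 3 need sSAP wording and at most one extra run. Section 9 allows changes to non-confirmatory analyses in the sSAP before unblinding. Section 8.10.5 already collects concomitant medication information after discontinuation; that this includes start dates is an assumption to confirm. The cost is slightly lower responder rates and a few more imputed or excluded values in supportive and exploratory analyses.
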